### 11.3.11 Handling of Missing Values

In this trial the imputation approach will be the Last Observation Carried Forward (LOCF) as we expect no or very few subjects to drop out. Overseas many trials have been conducted with LEO 90100 where the dropout rate was very low. There is no evidence to support that psoriasis is a different disease in Japan than is the rest of the world. This is consistent with the procedure for determining the primary endpoint for subjects who have substantial resolution of the target lesion before the end of 4 weeks of treatment.

Sensitivity analyses where missing values of the primary endpoint are imputed by either achieving or not achieving ‘overall improvement rate’, will be done. Imputation will be done for each treatment group separately and with two treatment groups and two outcomes, there will be four sensitivity analyses in total. These sensitivity analyses will define the range to which the result of the primary analysis would belong, in case no missing values had been present.

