## 6.2 Sample Size

A total of 180 subjects will be randomised in a 1:1 ratio to the two treatment groups, i.e. 90 in each treatment group in order to provide at least 80 subjects per group who complete the trial. It is anticipated that approximately 200 subjects will be screened in order to provide 180 randomised subjects.

The sample size is not based on power calculations, but is based on regulatory considerations, as 80 subjects per treatment group is the number that has been used for a similar trial in Japan to compare different topical formulations of the same active ingredient (28).

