### 11.2 Definition of Trial Analysis Sets

All subjects enrolled in the trial (i.e. subjects for whom informed consent has been obtained and who have been registered in a clinical trial) will be accounted for in the clinical trial report.

All randomised subjects are included in the full analysis set and will be analysed for efficacy. Exclusions from the full analysis set can be considered in special cases as described in ICH

E9, section 5.2.1., Full Analysis Set. Any exclusion of subjects from the full analysis set will be justified.

A per protocol analysis set will be defined by excluding subjects from the full analysis set who had less than 75% compliance or based on a review of protocol deviations with justification.

A safety analysis set will be defined by excluding randomised subjects who either received no treatment with IMP and/or for whom no post-baseline safety evaluations are available.

The decisions regarding inclusion/exclusion of subjects and/or subject data from the trial analysis sets will be documented in the analysis set definition document.

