### 11.3.10 General Principles

All significance tests will be two-sided using the 5% significance level. All confidence intervals will be presented with 95% degree of confidence.

An observed cases approach will be used for tabulations of data by visit (i.e. involving only those subjects who attended each specific visit).

Categorical data will be summarised using the number and percentage of subjects in each category and treatment group. Continuous data will be summarised using the mean, median, standard deviation (SD), minimum and maximum values. For laboratory data, the geometric mean and coefficient of variation will be included.

‘Baseline’ value is defined as the value from the latest assessment before treatment, i.e. at Visit 1 (Day 1) before randomisation.

Any changes from the statistical analysis planned in this clinical trial protocol will be described and justified in a protocol amendment/the statistical analysis plan and/or in the clinical trial report dependent on the type of deviation.

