6.8 General Principles

6.8.1 Handling of Drop-outs and Missing Values

A LOCF approach will be used to impute missing values at Visit 4 (end of week 4) for the primary endpoint as described in the CTP (section 11.3.11).

LOCF will be used to impute missing values for the analysis of change from baseline to Visit 4 (end of week 4) in the sum of total sign score and the analysis of change from baseline to Visit 4 (end of week 4) in change in score for the severity of each clinical sign.

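### Primary-endpoint LOCF ignores why Visit 4 is missing: an adverse-event withdrawal can count as a Week 4 responder, and subjects with no post-baseline assessment have no scoring rule

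*Protocol*

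**What the plan says.** Protocol 11.3.11 states that in this trial "the imputation approach will be the Last Observation Carried Forward (LOCF) as we expect no or very few subjects to drop out". It supports this with low drop-out in overseas trials, and adds that the approach agrees with how subjects who clear early are handled. SAP 6.8.1 repeats the rule: "A LOCF approach will be used to impute missing values at Visit 4 (end of week 4) for the primary endpoint". Neither section distinguishes between reasons for a missing value. The SAP's clinical argument, that relapse in the target area is not expected, is in 6.6.1, in the paragraph on subjects who finish early with substantial resolution.

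Four other parts of the plan matter here:

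- **Withdrawal.** Protocol 7.7 permits withdrawal for unacceptable adverse events, unacceptable efficacy, voluntary reasons and other reasons. It counts early clearers as completers.
- **Assessment.** General change is rated at Visits 2 to 4 (Protocol 8.12) and also at the unscheduled/early-withdrawal visit (schedule in 8.1).
- **Analysis set.** Protocol 11.2: "All randomised subjects are included in the full analysis set and will be analysed for efficacy". Exclusions are possible in special cases and must be justified.
- **Sensitivity analyses.** Protocol 11.3.11 plans four, setting missing values to success or failure separately in each group (SAP Tables EI1 to EI4).

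On numbers, Protocol 6.2 plans "90 in each treatment group in order to provide at least 80 subjects per group who complete the trial".

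**The concern.** The no-relapse argument fits a subject who stopped because the lesion had cleared. It does not cover a subject who was partly better and stopped because the treatment could not be tolerated. LOCF treats the two alike, so the second subject becomes a Week 4 success in the primary rate, odds ratio and p-value.

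Separately, the primary analysis is meant to include everyone randomised, but the plan does not say what outcome a subject has when nothing was assessed after baseline. One route to very early exit is written into the protocol: under 8.10, a subject whose Visit 1 laboratory results arrive after randomisation and meet an exclusion criterion is withdrawn. Whether such subjects count as failures or leave the denominator would be settled only at analysis.

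At stake are the level of each group's response rate and, if the arms lose subjects differently, the comparison itself.

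**Working it through.** **1. The plan's own figure.** Protocol 6.2: "A total of 180 subjects will be randomised in a 1:1 ratio to the two treatment groups", so 2 × 90 = 180. With at least 80 completers per group, the allowance is 90 − 80 = 10, and 10/90 = 11.1%. Conversely, 80/(1 − 10/90) = 90, but that is back-calculated and confirms only the arithmetic. Early clearers count as completers, so the 10 are other losses. Because "The sample size is not based on power calculations, but is based on regulatory considerations", the documents give no response rate, effect size or drop-out rate. Every rate used below is an assumption.

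**2. Tracing an adverse-event withdrawal.** The subject is rated 'moderately improved' at the last assessment. That rating alone meets the primary endpoint in 5.1. Visit 4 is missing, so 11.3.11 carries the last value forward, and the subject is a responder. Nothing in either document interrupts this chain.

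**3. Effect on one group's rate.** Let d be the number of subjects with a carried value and q the share whose last value is a response. LOCF minus non-response scoring = d × q / 90.

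| d | q = 0.5 | q = 1 |
|---|---|---|
| 1 | 0.6 points | 1.1 points |
| 2 | 1.1 | 2.2 |
| 5 | 2.8 | 5.6 |
| 10 | 5.6 | 11.1 |

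**4. Effect on the difference (foam − ointment).** Shift = (d_foam × q_foam − d_oint × q_oint)/90.

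- Equal d and equal q: the shift is 0.
- Unequal, assuming 80% response among completers in both groups, 10 foam and 2 ointment drop-outs, and q = 0.5. Responders among completers are 0.8 × 80 = 64 and 0.8 × 88 ≈ 70.
  - Non-response scoring: 64/90 v 70/90 = 71.1% v 77.8%, difference −6.7 points, Fisher p = 0.39.
  - LOCF: 69/90 v 71/90 = 76.7% v 78.9%, difference −2.2 points, p = 0.86.
  - Shift: (5 − 1)/90 = 4.4 points.

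Protocol 11.3.10 says "All significance tests will be two-sided using the 5% significance level", so neither result in this example is significant. The estimate moves; the conclusion does not.

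**5. No post-baseline assessment.** General change has no Visit 1 value. Visit 1 sign scores do exist, and inclusion criterion 5 requires at least 2 on each, so substantial resolution cannot be met at baseline. Carrying baseline forward would give a non-response; excluding the subject would shrink the denominator. For k such subjects and r responders, exclusion raises the rate by r/(90 − k) − r/90. With k = 3 and 80% response: 70/87 − 70/90 = 80.5% − 77.8% = 2.7 points. Over assumed response rates of 70% to 90%, the gap is 0.8 to 1.0 points for k = 1, 2.3 to 3.0 for k = 3, and 3.9 to 5.0 for k = 5.

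**6. What the four sensitivity analyses show.** The range of the difference across the four is:

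- 80% among completers in both groups, 2 drop-outs each: −2.2 to +2.2 points (p = 0.86 at the extremes).
- The same with 10 each: −11.1 to +11.1 (p = 0.11).
- 90% v 80%, 10 each: −2.2 (p = 0.85) to +20.0 (p = 0.001).

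With very few drop-outs the range is narrow. At the full allowance it can span different conclusions. There is also an ambiguity: SAP 6.6.1 describes the early clearers' values as LOCF imputation, so they could be read as missing in EI1 to EI4. Each clearer then set to failure would lower a group's rate by 1/90 = 1.1 points.

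**The case against.** The strongest reply has four parts.

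- **Drop-out is expected to be very low.** The margin of 10 per group protects a minimum of 80 completers and is not a forecast. This stands: the margin does not contradict the LOCF rationale, though the two sit awkwardly together, and 11.1 points is a ceiling.
- **The arms should lose subjects similarly.** They share active ingredients and concentrations, and a similar safety profile is expected (Protocol 3.4). With equal drop-out and equal carried response, the difference is untouched. This also stands. However, the trial is open and Protocol 3.3 expects better compliance with the foam, so unequal withdrawal cannot be ruled out.
- **Non-response scoring is already planned.** One of the four sensitivity analyses sets missing values in both groups to failure. That is correct, but the primary estimate, odds ratio and p-value stay on LOCF, and the set does not define whether early clearers are missing.
- **Failing every missing Visit 4 would overreach.** It would penalise subjects who merely missed the visit or left for unrelated reasons, and could itself bias the rates. This stands and limits the fix.

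Two stronger readings are tempting. A reader might infer that poor-efficacy withdrawals also become responders. The schedule calls for sign scores and general change at the early-withdrawal visit, so where that visit takes place such subjects will usually carry a non-response. The adverse-event route is the real one. A reader might also infer that subjects with no post-baseline visit cannot be scored or must leave the analysis. Step 5 shows that they can be scored, and Protocol 11.2 keeps them in the full analysis set unless an exclusion is justified. What is missing is a written rule.

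**Conclusion.** The point holds as a gap in a stated rule. LOCF can credit an adverse-event withdrawal as a Week 4 success, and a randomised subject with no post-baseline assessment has no defined outcome. The size for one group is up to 1.1 points per subject carried as a response, and at most 11.1 points at the full planning allowance.

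A reader might go further and conclude that LOCF biases the treatment comparison. The documents do not support that. The difference shifts only if drop-out or carried response differs between arms, and no rates are given. The 4.4-point shift in the worked example rests wholly on assumed inputs: 80% response among completers, a 10 v 2 split, and half of drop-outs carrying a response. For scale, the 95% confidence interval for the difference at 80% response and 90 per group has a half-width of about 1.96 × √(2 × 0.8 × 0.2/90) = 11.7 points. If drop-out is as low as the protocol expects, the practical effect will be small. This is a cheap improvement to make, not a defect that undermines the trial.

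**What to change.** In Protocol 11.3.11 and SAP 6.8.1:

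1. Keep carry-forward for subjects who complete early with substantial resolution.
2. In the primary analysis, score as not achieving overall improvement those who withdraw for adverse events or unacceptable efficacy, and those with no post-baseline assessment.
3. Keep LOCF for all missing Visit 4 values as a sensitivity analysis.
4. State that early completers with substantial resolution are not missing in Tables EI1 to EI4.

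Subjects who miss Visit 4 or leave for other reasons, but have a post-baseline rating, stay on LOCF.

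The cost is wording, plus the justification that Protocol 11.3.10 requires for a change to the planned analysis. No new data are needed, because 7.7 already has the reason for withdrawal recorded in the eCRF. Response rates will be slightly lower. The primary result will also depend on how the reason for withdrawal is classified, by site staff who know the treatment. The retained LOCF analysis and the four existing ones show how much that matters.

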## **5 Trial Endpoints**

### **5.1 Primary Endpoint**

The primary endpoint is 'overall improvement rate' for the target lesion at Visit 4 (end of Week 4), defined as 'substantial resolution' of clinical signs or at least 'moderately improved' in the general change in the target lesion. 'Substantial resolution' is defined as a clinical score for thickness and scaliness of 0 and a clinical score for redness of 1 or less in the severity of clinical signs of the target lesion.

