6.6 Analysis of Efficacy

6.6.1 Primary Efficacy Criteria

The primary endpoint will be analysed as described in the CTP (section 11.3.4).

In addition, the difference (LEO 90100 foam – Dovobet[®] ointment) in the proportion of subjects with overall improvement rate, its 95% confidence interval will also be presented. Refer to CTP (11.3.11) for the imputation method.

For subjects who completed the trial before 4 weeks of treatment due to achieving substantial resolution, use the latest available results for LOCF imputation. This approach of imputation is legitimate under the assumption of short exposure time and type of population included; a re-lapse on the disease in the target area will not be expected.

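### Are subjects who clear early and leave the trial counted as missing, and so as failures, in the four sensitivity analyses?

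*Protocol*

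**What the plan says.** Protocol 5.1 sets the primary endpoint "for the target lesion at Visit 4 (end of Week 4), defined as" substantial resolution of clinical signs or at least moderate improvement. Under Protocol 6.1 and 7.7, a subject whose target lesion reaches substantial resolution before the end of treatment completes the trial then.

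Protocol 11.3.11 chooses LOCF because few drop-outs are expected, and adds: "This is consistent with the procedure for determining the primary endpoint for subjects who have substantial resolution of the target lesion" before four weeks are up. It then plans the bounding analyses: "Sensitivity analyses where missing values of the primary endpoint are imputed by either achieving or not achieving" the endpoint. On their number it says that "with two treatment groups and two outcomes, there will be four sensitivity analyses in total", and on their purpose: "These sensitivity analyses will define the range to which the result of the primary analysis would belong", had nothing been missing.

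SAP 6.6.1 says: "For subjects who completed the trial before 4 weeks of treatment due to achieving substantial resolution, use the latest available results for LOCF imputation". Its reason is that a "re-lapse on the disease in the target area will not be expected". SAP 6.8.1 says: "A LOCF approach will be used to impute missing values at Visit 4 (end of week 4) for the primary endpoint". The four analyses appear in SAP Appendix I as tables EI1 to EI4, by title only.

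**The concern.** Read in sequence, the SAP sections seem to make the Week 4 value of an early clearer a missing value. The endpoint belongs to Visit 4, the subject has left before it, the SAP calls the value assigned to that subject an imputation, and SAP 6.8.1 says LOCF is what fills missing Visit 4 values. Protocol 11.3.11 then replaces missing endpoint values by success or failure and exempts nobody. A programmer who took LOCF away and imputed whatever was left blank would score some cleared subjects as failures.

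At stake is the meaning of EI1 to EI4. They are meant to bound what missing data could have done to the result. If they included subjects who met the response definition at their last assessment, the bounds would be wider than drop-out alone can explain. If early clearance differed between arms, they would also be shifted against the product that clears faster. Two programmers could produce different tables from the same text.

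**Working it through.** **Inputs.** Protocol 6.2: 90 randomised per arm. Protocol 11.3.11: four analyses. No document gives a drop-out rate, an early-clearance rate or an expected response rate. I therefore assume d=2 drop-outs per arm, c from 0 to 18 early clearers per arm, and 72 of 90 responders per arm with early clearers included. Protocol 6.2 randomises 90 to obtain at least 80 completers. That allows for 10 non-completers per arm (10/90 = 11.1%), but it is a recruitment allowance and not a limit.

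**The plan's own figure.** Two outcomes in each of two arms give 2 × 2 = 4 combinations, as stated. Imputing one arm at a time would also give four. Only the crossed version in general reaches the outer bounds, because the extremes need the arms at opposite outcomes, so the bounding purpose points to the cross. Three of its four cells have failure in at least one arm.

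**Width of the range.** Let k be the responders not subject to imputation and m the number imputed, by arm.

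- Largest difference: (k_foam + m_foam − k_oint)/90
- Smallest difference: (k_foam − k_oint − m_oint)/90
- Span: (m_foam + m_oint)/90, whatever the response rate

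With equal arms the range is ±m/90. Here m=d if early clearers are kept as responders, and m=c+d if they are counted as missing.

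| c per arm (d=2) | Kept as responders | Counted as missing | Extreme counts if missing | Fisher p |
|---|---|---|---|---|
| 0 | ±2.2 points | ±2.2 | 74 v 72 | 0.85 |
| 2 | ±2.2 | ±4.4 | 74 v 70 | 0.58 |
| 5 | ±2.2 | ±7.8 | 74 v 67 | 0.28 |
| 9 | ±2.2 | ±12.2 | 74 v 63 | 0.080 |
| 18 | ±2.2 | ±22.2 | 74 v 54 | 0.0016 |

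With d=10 and c=9 the range is ±11.1 against ±21.1 points. With unequal clearance (18 on foam, 9 on ointment, equal true response), failure in both arms gives 54/90 v 63/90, or −10.0 points, where keeping clearers as responders gives 0.

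**Effect on the primary analysis.** An early clearer has thickness and scaliness 0 and redness at most 1 at the last assessment. That meets the endpoint definition, so LOCF makes the subject a responder in table E1 whichever label is used.

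**Which reading the text supports.**

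- *Counted as missing:* the SAP's use of the word imputation (6.6.1) and its description of LOCF as filling missing Visit 4 values (6.8.1). Both passages concern the LOCF analyses, not EI1 to EI4.
- *Kept as responders:* Protocol 11.3.11 imputes missing values of the endpoint, and just before that it refers to a procedure that determines the endpoint for early clearers. An endpoint already determined is not missing. Protocol 6.5 and 7.7 define these subjects as completers. The reason given for the choice of LOCF is drop-out. SAP 6.6.1 expects no relapse. The schedule in Protocol 8.1 labels the last visit as Visit 4 or end of treatment.

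**The case for a change.** The best case for a change is that the gap is real and would cost only a few SAP sentences to close. No sentence gives the status of early clearers in EI1 to EI4. For laboratory samples, physical examination, pregnancy test and subject assessments, the protocol says that a subject completing at Visit 2 or 3 has them done then in place of Visit 4. Section 8.12, on the lesion scores that decide the endpoint, has no such rule. Completer status governs disposition, not imputation. The number of early clearers is not bounded by anything in the plan, and unequal clearance could tilt the failure/failure table.

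The silence stands, and so does the arithmetic under the unfavourable reading. The rest carries less weight. Lesion scores are already scheduled at Visits 2 and 3, whereas the laboratory samples, pregnancy test and subject assessments are not, so a substitution rule was less needed for the lesion (the physical examination, scheduled at every visit, is the exception). The larger widths rest on assumed counts. Clearing early means going from at least 2 on every sign to 0, 0 and at most 1 by the Week 1 or Week 2 visit, and at one or two clearers per arm the effect is small.

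The value carried forward is also not strictly observed at Week 4; it depends on the no-relapse assumption. An analyst who put early clearers into the worst-case bounds could defend that as a test of the assumption. The unfavourable reading would therefore give a wider and more conservative range, not a false primary result.

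**Conclusion.** The plan leaves a detail unstated, and analysts can fill it sensibly from what is there: early clearers keep their responder status, only other missing Visit 4 values are imputed, and EI1 to EI4 are the four foam/ointment outcome combinations. On that reading the range reflects drop-outs alone: ±2.2 points at an assumed two per arm, ±11.1 at ten.

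The unfavourable reading adds c/90 to each side, 1.1 points per early clearer per arm. How much that would be in practice cannot be said, because the documents give no clearance rate. It would not alter table E1, the data collected or the sample size, which is not power-based, and no decision rule refers to the four tables. A reader could also detect it, since table E12 and the listings of clinical signs and overall improvement show who cleared and when. No change to the plan is needed.

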### 13 Appendix 1: Protocol Summary

Name of finished/ investigational medicinal product	LEO 90100 foam
Name of active substance	Calcipotriol hydrate and betamethasone dipropionate
Title of trial/trial ID	Efficacy and safety of LEO 90100 foam in Japanese subjects with psoriasis vulgaris / LP0053-1422
Coordinating investigator	[name], PhD
Sponsor's name/ address	LEO Pharma A/S, Denmark, Ballerup. LEO Pharma K.K. is the sponsor of the clinical trial in Japan on behalf of LEO Pharma A/S. LEO Pharma K.K., Tokyo, Japan.
Estimated number of trial sites and distribution	Twenty trial sites in Japan
Trial period	Q1 2019 to Q3 2019
Main objectives and endpoints	
Objectives
 
Primary objective: To compare the efficacy of LEO 90100 foam with Dovobet® ointment in the treatment of psoriasis in Japanese subjects.
 
Secondary objective: To compare the safety of LEO 90100 foam with Dovobet® ointment in the treatment of psoriasis in Japanese subjects.
 
Endpoints
 
Primary endpoint: 'Overall improvement rate' for the target lesion at Visit 4 (end of Week 4), defined as 'substantial resolution' of clinical signs or at least 'moderately improved' in the general change in the lesion. 'Substantial resolution' is defined as a clinical score for thickness and scaliness of 0 and a clinical score for redness of 1 or less in the severity of clinical signs of the lesion.

	
Secondary endpoint:
 
Subjects with ‘overall improvement rate’ for the target lesion at Visits 2 and 3 (end of Weeks 1 and 2)
 
The change in the sum of the scores (total sign score) for the severity of the three clinical signs (thickness, scaliness, redness) from Visit 1 to Visit 4 (end of Week 4) for the target lesion.

Final collection of data for the primary endpoint	Visit 4 (end of Week 4)
Methodology	
A phase 3, national, multi-centre, 4-week, prospective, randomised, controlled, parallel-group, open trial of LEO 90100 foam versus Dovobet® ointment (each containing calcipotriol hydrate 52.2 µg/g [equivalent to 50.0 µg/g calcipotriol] plus betamethasone dipropionate 0.643 mg/g) in Japanese subjects with psoriasis vulgaris.
 
Each subject will have one target lesion of psoriasis identified on the body. Subjects will be randomised to treat psoriasis with either LEO 90100 foam or Dovobet® ointment for 4 weeks.

Number of subjects to be enrolled	A total of 180 subjects will be randomised in a 1:1 ratio to the two treatment groups, i.e. 90 in each treatment group in order to provide at least 80 subjects per group who complete the trial. It is anticipated that approximately 200 subjects will be enrolled in order to provide 180 randomised subjects
Main criteria for inclusion	
 
1. Japanese subjects aged 20 years or more
 
2. Clinical diagnosis of psoriasis vulgaris of less than or equal to 30% BSA (excluding any psoriasis on the face/skin folds/genitals)
 
3. A target psoriasis lesion on the body, of a minimum size of 10 cm^2 and scoring at least 2 (mild) for each of redness, thickness and scaliness
 
4. Females of childbearing potential must have a negative result for a urine pregnancy test at Day 1 (Visit 1) and must agree to use an adequate method of birth control
 

Main criteria for exclusion	
 
1. Use of systemic treatment with an effect on psoriasis
 
2. Use of UV therapy on full body or on the target lesion
 
3. Use of topical treatment on areas to be treated with trial medication
 

	
4. Topical treatment on areas other than treated areas with vitamin D analogues, immunosuppressants or strong/very strong corticosteroids
 
5. Skin diseases besides psoriasis on the areas to be treated with trial medication.
 
6. Disorders of calcium metabolism, hypercalcaemia, renal insufficiency, hepatic disorders, heart disease.

Investigational medicinal product	LEO 90100 foam (containing calcipotriol hydrate 52.2 µg/g [equivalent to 50.0 µg/g calcipotriol] plus betamethasone dipropionate 0.643 mg/g) applied to a target lesion and any other areas of psoriasis once daily
Investigational reference product	Dovobet ® ointment (containing calcipotriol hydrate 52.2 µg/g [equivalent to 50.0 µg/g calcipotriol] plus betamethasone dipropionate 0.643 mg/g) applied to a target lesion and any other areas of psoriasis once daily
Duration of treatment	
Screening period: up to 4 weeks
 
Treatment period: up to 4 weeks
 
Follow-up period (if required): up to 2 weeks

Main assessments	
The severity of each clinical sign (redness, thickness, scaliness) of the target lesion on a 9-point scale, from 0 = none to 4 = severe
 
The general change in the target lesion from baseline on 5-point scale (markedly improved, moderately improved, slightly improved, unchanged, aggravated)

Statistical methods	Fisher's exact test

